17.0 Ongoing Safety Monitoring during the Trial

The PI is primarily responsible for reviewing safety data which will be monitored on a continual basis throughout the performance of the study as well as conducting interim safety analyses 10, 20, and 30 study subjects have completed 84 days of the study (see *Safety Monitoring* and *Interim Safety Analysis* below).

The PI will monitor and provide recommendations concerning safety and tolerability based on his/her evaluation of emerging trends and risks in reported SAEs and AEs which capture abnormal vital signs, physical exam findings, and abnormal laboratory tests.

The PI will review all SAEs in real time and conduct appropriate reporting to the IRB and Vertex Pharmaceuticals as required, within 24 hrs at maximum.

The PI will make the following determinations with the site Investigator reporting the SAE:

- Does the reported adverse event meet one of the FDA's definitions for serious?
- Is the event unexpected?
- Is the event related to study drug?

18.0 Interim Analysis

18.1 Interim Safety Analysis

Interim safety analysis will include blinded review of AEs, ECGs, and safety labs by the PI and will be conducted after completion of 10, 20, and 30 subjects. The interim safety analysis will include an interim safety report prepared by the PI for all Co-Investigators to review. This report will include a summary of the following:

- Demographics and baseline characteristics
- Enrollment
- Adverse events
- Withdrawals
- Exacerbation and hospitalization rates

18.3 Interim Efficacy Analysis

No interim efficacy analyses are planned for the study.

19.0 Source Document Monitoring and Study Management

Source document review will be conducted by the investigative team. Prior to each interim safety analysis, an independent Research Coordinator will confirm source documentation and review findings with the primary Research Coordinator and PI, and document findings in the study binder. Paper source documentation will be used for the study and stored in a secure location. Data will be input into a study specific RedCap database upon completion of each study subject.

20.0 PK and PK/PD Analysis

Intensive PK Analysis will be conducted at UAB by Dr. [name]'s laboratory using LC/MS/MS method already established at our laboratory and described in the pilot study.¹² Calculated PK parameters include: area-under-the-curve (AUC₁₂), maximum plasma concentration (C_{max}), time to C_{max} (T_{max}), oral clearance (CL/F), terminal apparent distribution volume (V_z/F), and elimination half-life (t_{1/2}). Subsequently, intensive data and sparse plasma concentrations will be combined to create a population PK model to assess covariates, such as age, weight, sex, smoking status, etc. as previously conducted by our group for NIH and industry sponsored studies. PK/PD analyses between ivacaftor levels and CFTR activity in the sweat gland will reveal new insights into the degree that wild-type CFTR can be activated by the CFTR potentiator ivacaftor.

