Clinical Study Protocol

A Randomized, Double-blind, Phase 2, Placebo Controlled Study to Determine the Safety and Efficacy of Ivacaftor (VX-770) for the Treatment of Chronic Obstructive Pulmonary Disease (The Topic Trial)

9/2/2016

Principal Investigators: [name], MSPH

[name]

PROTOCOL SYNOPSIS

Title: A Randomized, Double-blind, Phase 2, Placebo Controlled Study to Determine the Safety and Efficacy of Ivacaftor (VX-770) for the Treatment of Chronic Obstructive Pulmonary Disease (The Topic Trial)

Lead Investigators: [name] MSPH
[name]
[name]
[name]
[contact]
Email: [contact]

[name] MD
[name]
[name]
[name]
[contact]
Email: [contact]

Clinical Phase Phase 2

Study Synopsis

General Description: The study is a Phase 2 Study to establish the safety and efficacy of the CFTR potentiator ivacaftor in patients with chronic obstructive pulmonary disease (COPD), chronic bronchitis, and acquired CFTR dysfunction as detected by sweat chloride analysis. The design is a pilot, randomized (3:1, active:placebo), double-blind, placebo-controlled study to determine the safety and efficacy of ivacaftor (VX-770). Approximately 40 subjects with COPD will be randomized (Figure 1).

Primary Objective:

1. Evaluate the safety of ivacaftor treatment in patients with COPD and chronic bronchitis
2. Evaluate the pharmacokinetics of ivacaftor in patients with COPD and chronic bronchitis

Secondary Objectives:

1. Measure the pharmacodynamics of ivacaftor on CFTR activity (Sweat Chloride, MCC) in COPD patients with chronic bronchitis
2. Measure the effect of ivacaftor treatment on clinical outcomes (spirometry, patient symptoms, 6 minute walk test) in COPD patients with chronic bronchitis

Primary Endpoint:

1. Safety as determined by adverse events, clinical laboratory values (serum chemistry, hematology, coagulation studies), standard digital ECGs, vital signs, and physical examinations

2. Pharmacokinetic parameters of ivacaftor in COPD subjects (8 hr day 1 PK and PK peak and trough concentrations on days 28, and 84. A random PK will be collected on day 56)

Secondary Endpoints:

1. Change in respiratory and peripheral CFTR activity as detected by sweat chloride and MCC respectively
2. Indicators of respiratory function and COPD health (Change in FEV₁% as detected by spirometry, secondary spirometry values (FVC%, FEV₁/FVC), 6 minute walk test

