- Uncontrolled Diabetes
- Recent (e.g 1year) arterial thrombotic events (peripheral arterial disease, thrombotic stroke)
- Clinically significant arrhythmias requiring anti-arrhythmic agent(s) or conduction abnormalities that in the opinion of the investigator that affect patient safety such as the abnormalities listed below (patients with stable coronary artery disease are eligible)
 - ♦ Angina symptoms
 - ♦ History of MI
 - ♦ Revascularization procedure in the last year prior to screening
 - ♦ Clinically significant congestive heart failure (known LVEF $\leq 45\%$, cor pulmonale, diastolic heart failure, etc)

Investigational Drug: Ivacaftor, 150 mg PO every 12 hrs (or matching placebo)

Schedule of Study Visits: The first dose of ivacaftor will be administered at the Day 1 visit. Ivacaftor will be taken twice daily, with 12 hours between each dose from day 1 through the morning dose of day 84. Study visits will occur at Screening (-28 to -1 days), Day 1, Day 28 (\pm 7), Day 56 (\pm 7), Day 84 (\pm 7), and Follow-up (14 \pm 7 days after the last dose of ivacaftor).

Outcome Measures:

Safety assessments: Assessments include tests used in clinical studies to monitor the safety of ivacaftor in CF, including adverse event reporting, clinical laboratory testing, physical exams, and spirometry. The PI will review all SAEs in real time and conduct appropriate reporting to the FDA and IRB, as required, within 24hrs at maximum. Interim safety analysis will include review of AEs and safety labs by the PI and will be conducted after completion of approximately 10, 20, and 30 subjects. Ocular exam will be performed at baseline unless known history of cataracts.

PK: PK/PD analyses between ivacaftor levels and CFTR activity in the sweat gland will reveal new insights into the degree that wild-type CFTR can be activated. Calculated PK parameters include: area-under-the-curve (AUC₁₂), maximum plasma concentration (C_{max}), time to C_{max} (T_{max}), oral clearance (CL/F), terminal apparent distribution volume (V_z/F), and elimination half-life (t_{1/2}). Subsequently, intensive data and sparse plasma concentrations will be combined to create a population PK model to assess covariates, such as age, weight, sex, smoking status, etc. as previously conducted by our group for NIH and industry sponsored studies.

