4.0 STUDY DESIGN

The study is a Phase 2 Study to establish the safety and efficacy of the CFTR potentiator ivacaftor in patients with chronic obstructive pulmonary disease (COPD), chronic bronchitis, and acquired CFTR dysfunction as detected by sweat chloride analysis. The design is a pilot, randomized (3:1, active:placebo), double-blind, placebo-controlled study to determine the safety and efficacy of ivacaftor (VX-770) in approximately 40 subjects with COPD.

Enrollment is planned at our single center, The University of Alabama at Birmingham. Patients will be randomized 3:1 to active drug (n=30) and placebo (10) to achieve the enrollment goal.

- A sufficient number of subjects will be screened to randomize up to 50 subjects to achieve 40 completed subjects to receive either ivacaftor 150 mg BID (n=30) or placebo (n=10) for 84 days.
- The schedule of assessments is shown in Table 1. The protocol design is shown in Figure 1.
- Ivacaftor and matching placebo will be orally administered as capsules according to the following guidelines:
 - Between study visit Day 1 and study visit Day 84, subjects will take 1 dose of study drug each day in the morning, beginning any time between 08:00 h (8:00 AM) and 12:00 h (12:00 PM). Whenever possible, subjects should take the study drug at the same time each day.

- On the study visit days when PK samples are collected (study visit Days 1, 28, 56, and 84), the study drug is to be taken by the subject while he/she is at the study site
- For visits after the Day 1 visit, subjects will be instructed to bring all remaining study drug materials to the site; study drug will be dispensed at each visit.
- Ivacaftor will be prepared and dispensed by an unblinded pharmacist.
- Subjects will be instructed to continue their standard COPD medication regimen.

Table 1. Schedule of Assessments ^a8 hr PK (pre, 1, 2, 4, 8, hr samples). ^b peak and trough PK only, ^crandom PK, ^donly if indicated.

Assessment	Screen (Day -28 to -1) Visit 1	Day 1	Day 28 (± 2)	Day 56 (± 2)	Day 84 (± 2)	Follow Up (Day 98 ± 2)
		Visit 2	Visit 3	Visit 4	Visit 5	Visit 6
Informed Consent	X					
Medical History & Concomitant Medications	X	X	X	X	X	X
Physical Examination	X	X	X	X	X	X
Safety Labs	X		X	X	X	X ^d
CFTR Genotyping	X					
Urine Pregnancy Test		X	X	X	X	X
Serum Pregnancy Test	X					
Blood Biomarker Collection		X	X	X	X	X
Spirometry	X	X	X	X	X	X
Sweat Chloride	X	X	X	X	X	X
MCC	X				X	
Patient report outcome questionnaires		X	X	X	X	X

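### Section 20.0 lists CL/F, Vz/F and half-life among the parameters calculated from the intensive PK, but the only intensive profile is 8 hours after the first dose and is not a sound basis for them

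*Combined protocol and SAP*

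**What the plan says.** The Protocol Synopsis makes pharmacokinetics both a primary objective and the second primary endpoint, and describes the sampling as "8 hr day 1 PK and PK peak and trough concentrations on days 28, and 84", plus a random sample on Day 56. Table 1 in Section 4.0 gives the detail. Day 1 is sampled pre-dose and at 1, 2, 4 and 8 h. Days 28 and 84 are "peak and trough PK only". A PK sample is also marked at follow-up, without a footnote.

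Section 20.0 opens with the intensive PK analysis and continues: "Calculated PK parameters include: area-under-the-curve (AUC₁₂), maximum plasma concentration (C_{max}), time to C_{max} (T_{max}), oral clearance (CL/F"). The same list goes on to name Vz/F and half-life. The next sentence reads: "Subsequently, intensive data and sparse plasma concentrations will be combined to create a population PK model to assess covariates". The synopsis repeats the parameter list and the model. Neither place names the visit, the method (non-compartmental or model-based) or an extrapolation rule for any parameter.

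The dosing interval is stated in two ways. The synopsis says "Ivacaftor will be taken twice daily, with 12 hours between each dose from day 1 through the morning dose of day 84", and Section 9.0 also has 12-hourly dosing. Section 4.0 says "subjects will take 1 dose of study drug each day in the morning".

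**The concern.** Six parameters are listed. The Day 1 profile observes two of them, Cmax and Tmax, as finely as the sampling times allow. AUC12 has no 12 h sample. CL/F, Vz/F and half-life need a terminal slope. Once the peak falls at 2 h or later, that slope comes from at most the 4 h and 8 h samples, with nothing to check it. If the peak is near 4 h, the first of those two samples is still at the peak, so the slope is too shallow and the half-life too long. No later visit has a full profile.

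These parameters would describe exposure in COPD. An artefact of the sampling window could be read as altered clearance in this population.

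**Working it through.** The plan gives no half-life, Tmax or PK precision target, so there is no stated figure to reproduce.

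**Inputs from the plan.** Sampling times 0, 1, 2, 4 and 8 h (Table 1); 30 active subjects (Section 4.0); follow-up about 14 days after the last dose.

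**Assumptions.** One-compartment oral model, first dose, half-life 6 to 16 h, Tmax 2 to 5 h. Dose and CL/F are set to 1, so the true AUC to infinity is 1.

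**Formulas.**
- C(t) = [ka·k/(ka − k)]·(e^(−kt) − e^(−ka·t)), with k = ln 2/half-life and ka solved from Tmax = ln(ka/k)/(ka − k)
- Terminal slope λ = ln(C4/C8)/4; estimated half-life = ln 2/λ
- Estimated AUC to infinity = trapezoid to 8 h + C8/λ; estimated CL/F = 1/that AUC
- Estimated AUC12 = trapezoid to 8 h + (C8/λ)(1 − e^(−4λ))

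**Worked case: true half-life 12 h, Tmax 4 h.** k = 0.0578 and ka = 0.671. The concentrations at 1, 2, 4 and 8 h are 0.0274, 0.0398, 0.0459 and 0.0395.
- C4/C8 = 1.160, so λ = 0.1484/4 = 0.0371 and the half-life reads 0.693/0.0371 = 18.7 h.
- The trapezoid to 8 h is 0.304. Adding 0.0395/0.0371 = 1.065 gives 1.369, so CL/F = 1/1.369 = 0.73 of truth.
- AUC12 = 0.304 + 1.065 × (1 − e^(−0.1484)) = 0.451, against a true 0.453: a ratio of 0.99.

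**Across the assumed range.**

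| Tmax | Half-life read when truth is 12 h | CL/F ÷ truth, via AUC to infinity (half-life 6-16 h) | CL/F ÷ truth, via dose/first-dose AUC12 (half-life 12 h) |
|---|---|---|---|
| 2 h | 12.1 h | 1.00-1.01 | 2.07 |
| 3 h | 13.2 h | 0.92-0.95 | 2.13 |
| 4 h | 18.7 h | 0.70-0.74 | 2.21 |
| 5 h | 44.1 h | 0.35-0.36 | 2.31 |

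- The part of AUC to infinity after 8 h is 43-77%.
- The Vz/F ratio is 1.01-1.72. The errors in CL/F and λ partly cancel.
- Dose/first-dose AUC12 overstates CL/F 1.4 to 2.8 fold over the whole range, whatever the Tmax.
- The 8-12 h segment is 22-34% of first-dose AUC12, yet the extrapolated AUC12 is 0.98-1.01 of truth.

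**Measurement noise, single profile.** Take a true 12 h half-life, no absorption bias, and an assumed 10% error per sample (log scale). Then ln(C4/C8) has mean 4 × 0.0578 = 0.231 and SD 0.10 × √2 = 0.141. The chance of no decline is Φ(−0.231/0.141) ≈ 5%. Among the other profiles, the log-ratio has 5th and 95th percentiles of about 0.049 and 0.467. The half-life, 2.773/log-ratio, therefore runs from about 6 h to about 57 h.

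**Follow-up sample.** At 14 days (336 h) and a 16 h half-life, the fraction left is 0.5^(336/16) ≈ 5 × 10⁻⁷. At 7 days, the early edge of the synopsis window, it is 0.5^(168/16) ≈ 0.07%.

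**The case against.** The strongest reply is that the plan already pools the intensive and sparse data in a population model. Steady-state samples on Days 28, 56 and 84 carry information on clearance, so model-based CL/F, volume, half-life and AUC12 are attainable. The synopsis also gives the parameter list without the sentence on intensive analysis. This stands as far as feasibility goes. It does not settle the plan as written: Section 20.0 puts the list under the intensive analysis, introduces the model afterwards, and states only covariate assessment as its purpose.

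A reader might infer more than the documents support:
- *That the profile cannot give AUC12.* It can, by extrapolation, with almost no bias in this model.
- *That most of the second primary endpoint is lost.* The synopsis names Day 1 PK and peak and trough concentrations, which are observed directly, as are Cmax and Tmax.
- *That half-life and clearance will be wrong.* The error is negligible at Tmax 2 h and small to moderate at 3 h. Serious bias needs a Tmax near or after 4 h, which the documents do not give.
- *That clearance will be overstated 1.4 to 2.8 fold.* This follows only if CL/F is dose over first-dose AUC12, a formula the plan does not state. The route through AUC to infinity errs the other way when Tmax is late.

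It is also fair that the 6 to 57 h range describes single profiles. With 30 active subjects and the same noise alone, the group median half-life has a 5th-95th percentile range of about 10 to 15.5 h. Averaging does not remove the bias from slow absorption, however.

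**Conclusion.** The point holds for three parameters. The Day 1 profile alone is not a sound basis for CL/F, Vz/F and half-life, and Section 20.0 read in order derives them from it. AUC12 is a lesser matter: it is extrapolated without a stated rule but is hardly biased. The profile's observed quantities are unaffected.

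The size of the bias depends on an assumed one-compartment model and on Tmax: close to nil at 2 h, and a half-life about 3.7 times too long (44/12) at 5 h for a true 12 h. Two weaknesses hold at any Tmax in the range: heavy extrapolation of AUC to infinity, and an imprecise two-point slope in individual profiles. Because the two possible routes to CL/F can err in opposite directions, the method should be fixed in advance.

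**What to change.** In Section 20.0 and the synopsis:
1. Report AUC0-8, Cmax and Tmax non-compartmentally from Day 1.
2. State that CL/F, apparent volume, half-life and steady-state AUC12 come from the population model, fitted to Day 1 plus the Day 28, 56 and 84 samples, with actual dose and sample times.
3. If first-dose AUC12 is also reported, label it as extrapolated beyond 8 h.
4. Do not rely on the follow-up sample for the terminal phase; essentially no drug would remain by then under the assumed half-lives.
5. Reconcile the once-daily statement in Section 4.0 with the 12-hourly statements in the synopsis and Section 9.0, so that steady-state AUC12 and trough are defined.

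The cost is wording: the model and all samples are already planned, and no visits or subjects are added. The downside is that these parameters become model-based rather than directly calculated.
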